#### 6.1.3. Primary Analysis of the Primary Efficacy Endpoint

The hazard ratio of COVID-19 related hospitalization or all-cause death between the two treatment groups will be estimated using a Cox model with stratification factors as covariates.

If a participant prematurely discontinues from the study prior to Day 28 or the hospitalization status is missing, the participant is censored at last study date or day 28 whichever is earlier. If a participant has a COVID-19 related hospitalization first and then dies, then date of the COVID-19 related hospitalization and status will be used for the primary analysis for this participant. If a participant has a non COVID-19 related hospitalization first and then dies without experiencing a COVID-19 related hospitalization, then date of the death and status will be used for the primary analysis for this participant.

The hazard ratio, p-value, 95% CI for the hazard ratio from Cox model, and proportion of COVID-19 related hospitalization or all-cause death at Day 28 from Kaplan-Meier estimate will be provided.

The FAS will be the primary analysis set for efficacy endpoint evaluation. The primary endpoint may be analyzed for each of the subgroups defined in Section 3.3.

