    - Symptoms scored as 2 or higher at baseline are scored as 0 or 1 at postbaseline, AND
    - Symptoms scored as 1 at baseline are scored as 0 at postbaseline, AND
    - for two consecutive days.
  - Time to alleviation of baseline COVID-19 symptoms is defined (in days) as:

First Date of the two consecutive dates achieving alleviation - First dose Date + 1

If a participant has not achieved symptom alleviation at last FLU-PRO Plus assessment or early discontinuation of study, the participant will be censored at last FLU-PRO Plus assessment date. Last assessment date is the last date when at least one of the baseline symptoms is assessed.
- Worsening after alleviation of baseline COVID-19 symptoms
  - The worsening after alleviation of baseline COVID-19 symptoms is defined as:
    - For a participant who has achieved alleviation of baseline COVID-19 symptoms
    - If any symptom scored as 2 or higher at baseline is scored as 2 or higher postbaseline after achieved alleviation, or
    - Any symptom scored as 1 at baseline are scored as 1 or higher postbaseline after achieved alleviation.
- Proportion of participants progressing to requiring oxygen supplementation by Day 28

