### 6.2.1. Analysis of Secondary Endpoints

The FAS will be the primary analysis set for secondary endpoints. The mFAS will be used for secondary endpoints of composite endpoint of COVID-19 related MAVs or death.

All-cause mortality by Day 28 will be compared between the 2 treatment groups using the Fisher exact test. If a participant prematurely discontinues from the study prior to Day 28 or the Death status is missing, the participant will not be included in the analysis.

The secondary endpoint of COVID-19 related hospitalization or all-cause death by Day 14, COVID-19 related MAVs or death by Day 28, and COVID-19 related MAVs or death by Day 14 will be analyzed using the same method as used for the primary endpoint, described in Section 6.1.3.

The proportion of participants hospitalized (COVID-19 related) by Day 28 will be estimated using the Kaplan-Meier method and compared between the 2 treatment groups using a log-rank test. Hazard ratio and two-sided 95% CI estimated using the Cox regression with baseline stratification factors as covariates will be provided.

Number and percentage of participants progressing to requiring oxygen supplementation by Day 28 will be summarized and compared between treatment groups using the Fisher Exact test. Participants discontinued from the study before progressing to requiring oxygen supplementation will be considered as not requiring oxygen supplementation.

The Kaplan-Meier product limit method will be used to estimate and log-rank test will be used to compare treatment groups for the time to alleviation of baseline COVID-19 symptoms. Hazard ratio and two-sided 95% CI estimated using the Cox regression with baseline stratification factors as covariates will be provided. Number and proportion of participants with worsening after alleviation of baseline COVID-19 symptoms will be summarized.

Time-weighted average change in SARS-CoV-2 viral load from baseline to Day 7 will be summarized by treatment groups and compared between treatment groups using an ANCOVA model with baseline viral load as covariate, the analysis will be based on the Virology Analysis Set.

CC1

[REDACTED]

[REDACTED]

[REDACTED]

[REDACTED]

[REDACTED]

[REDACTED]

[REDACTED]

[figure not shown]
[REDACTED]

[REDACTED]

CCI

CCI

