- h Obtain ALT (and AST where available), serum creatinine, and creatinine clearance (calculated using Cockcroft-Gault or Schwartz formula; see Protocol Section 6.7.2) if not available within 90 days of screening, using a local laboratory.
- i Chemistry: alkaline phosphatase, AST, ALT, total bilirubin, total protein, albumin, lactate dehydrogenase, creatine phosphokinase, bicarbonate, blood urea nitrogen, calcium, chloride, creatinine, glucose, lipase, magnesium, phosphorus, potassium, sodium, uric acid.
- j Hematology: Complete blood count with differential.
- k Coagulation: INR, PT, aPTT
- l [REDACTED]
- m Urine pregnancy test will only be done for women of childbearing potential.
- n Nasopharyngeal swab and sputum samples will be collected and stored for SARS-CoV-2 RT-qPCR and potential resistance testing.
- o [REDACTED]
- p [REDACTED]
- q [REDACTED]
- r Medically attended visit information includes any interactions with health care professionals other than study staff or designees including hospitalization; in-person emergency, urgent, or primary care visits; or any other in-person visit attended by the participant and a health care profession. Identify the nature and cause of the visit.
- s FLU-PRO Plus questionnaire should be completed daily from Day 1 through Day 14 (if available).
- t Only AEs, symptom assessment, medically attended visit information, and concomitant medications review are needed if the visit is done by phone.

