#### **Events with Completely Missing Onset Date**

An AE with a completely missing onset date is defined as TEAE if end date meets any of the 3 criteria specified above.

- 10) The precision in reporting numerical values should be as follows:

Raw measurements will be reported the same as the data captured electronically or on the eCRF for all but hematology and chemistry values.

Standard deviation and standard error will be reported to one more significant decimal place than the raw measurement.

Mean, median, minimum, Q1, Q3, and maximum will be reported to the same number of decimal places of the raw measurements.

Exceptions may be considered; for example, if more than 4 significant digits are provided for the measurement.

Precision for derived parameters as follows:

Parameters	Decimal Places
log 10 of SARS-CoV-2 viral load	2
Time-weighted average change in SARS-CoV-2 viral load	2
BMI	2
CCI	

- 11) Last dose date is not expected to be missing. However, if last dose date is missing, it will be imputed using the maximum of non-missing, non-zero dose, study drug start and stop dates.
- 12) Incomplete death dates will be imputed as the maximum of the study drug start dates, study drug end dates, clinic or phone visit dates (lvis28dt), laboratory visit dates (llab28dt), including the 28-day follow-up visit date plus 1.
- 13) Censoring rules

Time to hospitalization/death: If a participant prematurely discontinues from the study prior to Day 28 or the hospitalization status is missing, the participant is censored at last study date or day 28 whichever is earlier.

Time to negative SARS-CoV-2 viral load, participants are censored at the last assessment day and participants are required to have at least one postbaseline assessment.

Time to alleviation of baseline COVID-19 symptoms:

- For overall baseline symptom alleviation, participants are censored at the last assessment day that at least one of the baseline symptoms was assessed. For baseline symptom alleviation for each domain, participants are censored at the last assessment day that at least one of the baseline symptoms within that domain was assessed

- 14) Graded Laboratory Abnormalities Summary

The following labels will be used for laboratory abnormalities and Grade 3 or 4 laboratory abnormalities summary tables and listings:

Battery	Lab Test Label Used in I-labtox Listing	Toxicity Direction	Lab Test Label Used in t-labtox Table
Hematology	Hemoglobin	Decrease	Hemoglobin (Decreased)

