#### 4. Tim to alleviation of baseline symptoms

First day of participant level alleviation status equals Yes. If a participant has not achieved symptom alleviation at last FLuPRO assessment, the participant will be censored at the date of last FLUpro assessment. For symptom alleviation of a domain, the last assessment date is only among those baseline symptoms within the domain.

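### Time to symptom alleviation has no separate rule for participants who die unalleviated or whose diary stops at a COVID-19 hospitalization, so their censoring is informative; the effect is modest

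*SAP*

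**What the plan says.** SAP Section 6.2 covers a participant who has not reached alleviation by the last questionnaire or by early study discontinuation: "the participant will be censored at last FLU-PRO Plus assessment date". It defines that date: "Last assessment date is the last date when at least one of the baseline symptoms is assessed". Two places in SAP Appendix 2 repeat the rule. In item 13 (censoring rules), "participants are censored at the last assessment day that at least one of the baseline symptoms was assessed". In item 18, part 4, "the participant will be censored at the date of last FLUpro assessment". None of the three mentions death or hospitalization.

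SAP Section 6.2.1 estimates the curves by Kaplan-Meier, says that a "log-rank test will be used to compare treatment groups for the time to alleviation of baseline COVID-19 symptoms", and adds a Cox hazard ratio. Protocol Section 8.5.2 only assigns the log-rank test to time-to-event endpoints in general.

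The questionnaire is scheduled daily from Day 1 to Day 14, where available (Protocol Section 6.4; procedures tables in both documents). Neither document says whether it continues in hospital.

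SAP Section 3.5 classes every efficacy endpoint except the primary as exploratory, tested two-sided at 5% without multiplicity adjustment.

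**The concern.** Kaplan-Meier, log-rank and Cox require that a censored participant has the same later prospects as those still under observation. That is false for someone who dies on Day 6 with symptoms, and doubtful for someone admitted on Day 6 whose diary ends there, because admission marks worsening.

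The trial's own hypothesis is that remdesivir reduces these events, so this censoring would be more frequent on placebo. The placebo curve would then be inflated more than the remdesivir curve, and part of any real difference would be lost. A reader would also take the Day 14 Kaplan-Meier percentage as the share who recovered, and it would be too high in both arms.

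The SAP deals with such events elsewhere. For the primary endpoint, when a participant dies after a hospitalization not related to COVID-19, "then date of the death and status will be used for the primary analysis for this participant". For viral load, samples from the start of additional COVID-19 treatment are dropped. The symptom endpoint has no comparable rule.

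**Working it through.** **Planning inputs.** Protocol Section 8.9 and SAP Section 1.3 assume a hospitalization or death rate of 12% on placebo and 6.6% on remdesivir. These reproduce the plan's figures for the primary endpoint: HR = ln(1 − 0.066)/ln(1 − 0.12) = 0.534; events = 1264 × 0.95 × 0.093 = 111.7; power = Φ(|ln 0.534| × √(111.7/4) − 1.96) = 91.2%, against a stated figure above 90% (R² = 0 assumed). The documents state no power, effect size or alleviation rate for the symptom endpoint.

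**Participants who could be exposed to the rule.** SAP Section 2.1.1 gives 584 randomized, about 292 per arm. At planning rates: 292 × 0.12 = 35 placebo and 292 × 0.066 = 19 remdesivir failures. This is an upper count, because the rates run to Day 28 and the diary to Day 14.

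**Model (assumptions, not document figures).** Let f be the failure share in an arm and p the share of non-failures who alleviate by Day 14.
- Non-failures alleviate with a constant daily probability h = 1 − (1 − p)^(1/12) over Days 2-13.
- No failure alleviates by Day 14.
- Each failure's diary stops on a day spread evenly over Days 3-9.

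Let S be the share of non-failures not yet alleviated and g the share of failures whose diary is still running that day.
- SAP rule: daily hazard = (1 − f)·S·h / [(1 − f)·S + f·g].
- Failures retained: set g = 1 to Day 14. The Kaplan-Meier result is then (1 − f)·p.
- The large-sample Cox HR solves the Breslow score equation for the two arms. HR above 1 means faster alleviation on remdesivir.

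**Day 14 alleviation, planning rates, p = 60%, no drug effect on symptoms among non-failures.**

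| | Placebo | Remdesivir | Difference |
|---|---|---|---|
| SAP rule | 57.6% | 58.7% | 1.1 points |
| Failures retained | 0.88 × 0.60 = 52.8% | 0.934 × 0.60 = 56.0% | 3.2 points |

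The SAP rule overstates alleviation by 57.6 − 52.8 = 4.8 points on placebo and 58.7 − 56.0 = 2.7 points on remdesivir.

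**Hazard ratios.**

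| Scenario | SAP rule | Failures retained |
|---|---|---|
| 12% vs 6.6%, p = 40-60%, no symptom effect | 1.03-1.04 | 1.08-1.09 |
| Same, p = 60%, only half of failures stop the diary | 1.06 | 1.09 |
| Halved rates (6% vs 3.3%), p = 40-60% | 1.02 | 1.04 |
| Halved rates, half of failures stop the diary | 1.03 | 1.04 |
| 12% vs 6.6%, HR 1.2 among non-failures | 1.23 | 1.28 |
| Halved rates, HR 1.2 among non-failures | 1.21 | 1.23-1.24 |

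**Direction.** With equal failure rates (12% in both arms) and no symptom effect, both rules give HR 1.00. With equal rates, HR 1.3 among non-failures, p = 60% and diary stops over Days 3-10, the SAP rule gives 1.28 and retention 1.26. The pull toward 1 therefore depends on remdesivir preventing failures.

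**The case against.** The strongest reply is that the documents do not say the diary stops at admission. Visits may be remote (Protocol Section 6.1), hospitalization is not listed as a reason to leave the study, and Protocol Section 6.6 asks that those who stop dosing stay in follow-up. A hospitalized participant who keeps answering without alleviating is already followed to Day 14. This stands, and it limits the point to deaths and to hospitalizations where the diary does end early.

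A reader might also infer that hospitalization is by definition a failure to alleviate. The documents do not support that. Alleviation is two consecutive days of sufficiently reduced baseline symptom scores, and hospitalization is at least 24 hours of acute care. Someone admitted on Day 3 and discharged on Day 5 could alleviate by Day 12. If the diary stops, alleviation is unknown, and counting it as not achieved is a choice.

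Third, retention brings the hospitalization effect into a symptom endpoint, although that effect is already tested as the primary endpoint. In the scenario with no symptom effect, the HR of 1.08-1.09 arises entirely this way. This is fair: retention answers a different question, namely who actually recovered by Day 14, and the SAP should say so. It does not rescue the present rule, which leaves deaths and diary cessation unaddressed.

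Finally, event rates were probably below plan. SAP Section 2.3 cites lower hospitalization rates, and SAP Section 6.4 says very few participants progressed to oxygen. The halved-rate rows are therefore more relevant than the planning-rate rows, although halving is itself an assumption.

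**Conclusion.** The point holds in a limited form. As written, the rule censors informatively for any death before Day 14 without prior alleviation, and for any hospitalized participant whose diary stops early. It overstates alleviation in both arms and, where remdesivir prevents these events, moves the hazard ratio toward 1.

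The size is modest: 1.03-1.04 instead of 1.08-1.09 at planning rates with every failure's diary stopping, and about 1.02 instead of 1.04 at halved rates. Both rest on assumed alleviation of 40-60% among non-failures and on no failure alleviating by Day 14.

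A reader might infer that all hospitalized participants are removed at admission, or that the rule could create a false benefit for remdesivir. The documents do not support the first, and the calculation does not support the second: where remdesivir has fewer failures, the bias runs against it. The endpoint is exploratory, but it serves a stated secondary objective and is tested at 5%, so the gap is worth closing. Redacted text after SAP Section 6.2.1 cannot be checked; the visible rules for this endpoint look complete.

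**What to change.** Amend SAP Section 6.2, Appendix 2 item 13 and Appendix 2 item 18 part 4 together:
- A participant who dies before alleviation stays at risk as not alleviated and is censored at Day 14.
- A participant with a COVID-19 related hospitalization before alleviation is followed on any later diary data. Confirmed later alleviation is an event on its date; otherwise the participant is censored at Day 14 as not alleviated.
- Other dropouts keep last-assessment censoring.
- The current rule, applied to everyone, is reported as a sensitivity analysis.
- Censoring before Day 14 is tabulated by arm and reason.

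The hospitalization and death data are already collected, so the cost is a short change to the censoring text, one rerun and one table. SAP Section 1 allows this before database finalization; a later change would be documented in the study report. The downside to state is that the endpoint then counts death, and hospitalization with no later diary evidence of recovery, as non-alleviation, so it partly reflects the hospitalization effect.

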### 6.2.1. Analysis of Secondary Endpoints

The FAS will be the primary analysis set for secondary endpoints. The mFAS will be used for secondary endpoints of composite endpoint of COVID-19 related MAVs or death.

All-cause mortality by Day 28 will be compared between the 2 treatment groups using the Fisher exact test. If a participant prematurely discontinues from the study prior to Day 28 or the Death status is missing, the participant will not be included in the analysis.

The secondary endpoint of COVID-19 related hospitalization or all-cause death by Day 14, COVID-19 related MAVs or death by Day 28, and COVID-19 related MAVs or death by Day 14 will be analyzed using the same method as used for the primary endpoint, described in Section 6.1.3.

The proportion of participants hospitalized (COVID-19 related) by Day 28 will be estimated using the Kaplan-Meier method and compared between the 2 treatment groups using a log-rank test. Hazard ratio and two-sided 95% CI estimated using the Cox regression with baseline stratification factors as covariates will be provided.

Number and percentage of participants progressing to requiring oxygen supplementation by Day 28 will be summarized and compared between treatment groups using the Fisher Exact test. Participants discontinued from the study before progressing to requiring oxygen supplementation will be considered as not requiring oxygen supplementation.

The Kaplan-Meier product limit method will be used to estimate and log-rank test will be used to compare treatment groups for the time to alleviation of baseline COVID-19 symptoms. Hazard ratio and two-sided 95% CI estimated using the Cox regression with baseline stratification factors as covariates will be provided. Number and proportion of participants with worsening after alleviation of baseline COVID-19 symptoms will be summarized.

Time-weighted average change in SARS-CoV-2 viral load from baseline to Day 7 will be summarized by treatment groups and compared between treatment groups using an ANCOVA model with baseline viral load as covariate, the analysis will be based on the Virology Analysis Set.

CC1

[REDACTED]

[REDACTED]

[REDACTED]

[REDACTED]

[REDACTED]

[REDACTED]

[REDACTED]

[figure not shown]
[REDACTED]

[REDACTED]

CCI

CCI

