## **8.5.2. Secondary Analyses**

The secondary endpoint of COVID-19 related hospitalization or all-cause death by Day 14, COVID-19 related MAVs (medical visits attended in person by the participant and a health care professional) or death by Day 28, and COVID-19 related MAVs (medical visits attended in person by the participant and a health care professional) or death by Day 14 will be analyzed similarly as in the primary analysis. The all-cause mortality at Day 28 will be compared between the 2 treatment groups using a Fisher exact test. The proportion of participants hospitalized by Day 28 and the proportion of participants progressing to requiring oxygen supplementation by Day 28 will be estimated using the Kaplan-Meier method and compared between the 2 treatment groups using a log-rank test. Other endpoints of interest related to proportion of participants will be compared between treatment groups using a chi-square test or Fisher exact test. Endpoints that are measured as time to first event will be compared between treatment groups using the log-rank test and continuous endpoints will be compared between treatment groups using a Wilcoxon rank sum test or analysis of variance model.

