### **3.5. Multiple Comparisons**

There will be no multiplicity adjustment in the final analysis. Efficacy will be evaluated using the primary efficacy endpoint at the significance level of 0.05. All other efficacy endpoints are exploratory in nature and will be tested using 2-sided tests at the 5% significance level without multiplicity adjustment.

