### 3.8. Analysis Visit Windows

#### 3.8.1. Definition of Study Day

Study day will be calculated from the first dosing date of study drug and derived as follows:

- For postdose study days: Assessment Date – First Dosing Date + 1
- For days prior to the first dose: Assessment Date – First Dosing Date

Therefore, study day 1 is the day of first dose of study drug administration.

**Last Dose Date** is defined as the maximum, nonmissing, nonzero dose end date of treatment recorded on the Study Drug Administration eCRF form with “Study Drug Permanently Withdrawn” box checked for participants who prematurely discontinued or completed study drug according to the Study Drug Completion eCRF. Refer to [Appendix 2](#) for missing date imputation, if necessary.

**Last Study Date** is the latest of the study drug start dates and end dates, the in-person or phone visit dates, the vital sign or respiratory status collection dates, Flu-PRO Plus questionnaire collection date and the laboratory collection dates, including the 28-day follow-up visit date, and the death date (if applicable, only for participants who prematurely discontinued study according to the Study Completion eCRF).

**Baseline value** is defined as the last value obtained on or prior to the first dose date (and time, if available) unless otherwise specified (see Section [3.8.3](#)).

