## 4. SUBJECT DISPOSITION

### 4.1. Subject Enrollment and Disposition

The number and percentage of participants randomized at each investigator site will be summarized by treatment group and overall using the Safety Analysis Set and All Randomized Analysis Set. The number and percentage of participants enrolled by randomized stratum will be summarized using stratum assignment captured in the IXRS. Discrepancy between IXRS and clinical database will be noted if applicable. The denominator for this calculation will be the number of participants in the Safety Analysis Set.

The summary of subject disposition will be provided by treatment group and overall for all screened participants. This summary will include the number of participants screened, screen failure participants who were not randomized, participants who met all eligibility criteria and were not randomized, participants randomized, participants randomized but never treated, participants in the Safety Analysis Set, participants in the modified FAS and participants in the FAS.

In addition, the number and percentage of the participants in the following categories will be summarized:

- Completed randomized treatment on study drug as recorded on the Study Drug Completion form
- Prematurely discontinuing study drug prior to completion with summary of reasons for discontinuing study drug as recorded on the Study Drug Completion form
- Completed study
- Prematurely discontinuing from study (with summary of reasons for discontinuing study) as recorded on the Study Completion form

The denominator for the percentages of participants in each category will be the number of participants in the Safety Analysis Set.

No inferential statistics will be generated. A data listing of reasons for premature study drug/study discontinuation will be provided.

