#### 6.1.4. Secondary Analyses of the Primary Efficacy Endpoint

Sensitivity analyses maybe conducted using the following alternative approaches for the primary endpoint.

- A CMH test including baseline stratification factors as strata for the statistical comparison between the two treatment groups. If a participant prematurely discontinues from the study prior to Day 28 with no event before discontinuation or the hospitalization/death status is missing, the participant will be considered as with no hospitalization/death.

The analysis is for the purposes of evaluating the robustness of the estimates of the primary analysis.

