### 7.1.7. Summaries of Adverse Events and Deaths

Treatment-emergent AEs will be summarized based on the Safety Analysis Set.

The number and percentage of participants who experienced at least 1 TEAE will be provided and summarized by SOC, High lever term (HLT), PT, and treatment group. For other AEs described below, summaries will be provided by system organ class, PT, and treatment group:

- Grade 3 or higher treatment-emergent AEs
- All treatment-emergent study drug-related AEs
- Grade 3 or higher treatment-emergent study drug-related AEs
- All treatment-emergent SAEs
- All treatment-emergent study drug-related SAEs
- All treatment-emergent AEs that caused premature discontinuation from study drug

TEAE and study drug related TEAE will summarized by system organ class, PT, Severity and treatment group.

A brief, high-level summary of the number and percentage of participants who experienced at least 1 TEAE in the categories described above, and treatment emergent deaths will be provided by treatment group. Treatment-emergent death refers to deaths that occurred between the first dose date and the last dose date plus 30 days (inclusive).

Multiple events will be counted only once per participant in each summary. Adverse events will be summarized and listed first in alphabetic order of SOC and HLT within each SOC (if applicable), and then by PT in descending order of total frequency within each SOC. For summaries by severity grade, the most severe grade will be used for those AEs that occurred more than once in an individual participant during the study.

In addition to the above summary tables, all treatment-emergent AEs, treatment-emergent AEs with Grade 3 or higher, treatment-emergent study drug-related AEs, and treatment-emergent study drug-related AEs with Grade 3 or higher, will be summarized by PT only, in descending order of total frequency.

In addition, data listings will be provided for the following:

- All AEs
- Study-Drug-Related AEs
- AEs with severity of Grade 3 or higher
- SAEs

- Study-Drug-Related SAEs
- Deaths
- AEs leading to premature discontinuation of study drug

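### Taken literally, the Day 28 mortality rule drops anyone who left the study early, including participants known to have died, so deaths could vanish from the Fisher test

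*SAP*

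**What the plan says.** Protocol 8.5.2 sets the test and attaches no exclusion to it: "The all-cause mortality at Day 28 will be compared between the 2 treatment groups using a Fisher exact test". SAP 6.2.1 keeps the test ("All-cause mortality by Day 28 will be compared between the 2 treatment groups using the Fisher exact test") and then adds a rule on who is left out: "If a participant prematurely discontinues from the study prior to Day 28 or the Death status is missing, the participant will not be included". SAP 6.4, which lists efficacy changes from the protocol, covers only the oxygen supplementation endpoint.

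Four other parts of the SAP bear on how that rule would work:

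- **3.8.1, Last Study Date.** The dates that feed this variable include "the death date (if applicable, only for participants who prematurely discontinued study according to the Study Completion eCRF".
- **4.1, disposition.** Study status has two categories: completed, and "Prematurely discontinuing from study (with summary of reasons for discontinuing study) as recorded on the Study Completion form".
- **6.1.4, sensitivity analysis of the primary endpoint.** The similar rule is qualified: "If a participant prematurely discontinues from the study prior to Day 28 with no event before discontinuation".
- **7.1.7, safety.** "Treatment-emergent death refers to deaths that occurred between the first dose date and the last dose date plus 30 days (inclusive".

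SAP 3.5 sets the standing of the endpoint: "All other efficacy endpoints are exploratory in nature".

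**The concern.** In a mortality analysis, a rule for unknown outcomes must not remove known ones. The 6.2.1 rule has two conditions joined by *or*. Missing death status is the second, so the only people the first can add are those whose death status is not missing. Some of them will have withdrawn alive, and leaving them out is reasonable. The rest may be people who died and whose study participation ended for that reason. The sentence treats both groups alike.

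Followed as written, the rule could take some or all deaths out of the numerator and denominator of a comparison that the protocol lists as a secondary endpoint. Two competent programmers could build different mortality tables from the same text. The mortality table could also disagree with the treatment-emergent death summary for no reason that a reader could see.

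**Working it through.** The plan states no mortality rate, death count or power for this test, so there is no figure to reproduce. The check sets the passages side by side and then sizes the effect on assumed counts.

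**Step 1. Can a death meet the exclusion condition?** No passage says outright that death is recorded as premature discontinuation, and the Study Completion eCRF is not available. Two passages point that way.

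- SAP 3.8.1 uses the death date only for participants recorded as having left the study early. That makes sense only if deaths can be found in that category.
- SAP 4.1 offers two study-status categories. A participant who dies before Day 28 must fall into one of them, and completed is the less natural choice.

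**Step 2. Is a known death protected somewhere else?**

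| Place | Analysis | Protection for a recorded death |
|---|---|---|
| SAP 6.1.3 | Primary Cox model | Yes: the text after the censoring rule says which date and status to use when a participant dies |
| SAP 6.1.4 | CMH sensitivity analysis | Yes: limited to those without an earlier event |
| SAP 6.2.1 | Day 28 mortality, Fisher test | None |
| SAP 6.4 | Changes from protocol | Does not mention this rule |
| SAP Appendix 2, item 13 | Censoring for time to hospitalization/death | Does not cover the Fisher test |

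**Step 3. Direction.** If an arm of *n* has *d* deaths and the rule removes *k* of them, the proportion goes from d/n to (d − k)/(n − k). For 0 < k ≤ d < n this is always smaller. Removing deaths can therefore only understate mortality compared with counting them.

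**Step 4. Size.** Inputs: 584 randomized (SAP 2.1.1) and 1:1 allocation (SAP 1.2). An even split is assumed, giving 292 per arm, and the death counts are hypothetical. The test is two-sided at 0.05 (SAP 3).

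For *a* deaths in one arm and none in the other, with equal arms of *n*, the two-sided Fisher p-value is 2 × C(n, a) / C(2n, a). For a = 6:

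2 × (292 × 291 × 290 × 289 × 288 × 287) / (584 × 583 × 582 × 581 × 580 × 579) = 0.030.

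| Deaths, placebo vs RDV | p, deaths counted | p, all deaths excluded |
|---|---|---|
| 2 vs 0 | 0.499 | 1 |
| 3 vs 0 | 0.249 | 1 |
| 4 vs 0 | 0.124 | 1 |
| 5 vs 0 | 0.061 | 1 |
| 6 vs 0 | 0.030 | 1 |
| 6 vs 1 | 0.123 | 1 |
| 8 vs 1 | 0.038 | 1 |

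The last column is the extreme case in which every death is dropped and the table becomes 0 versus 0. In the 6 versus 0 row, the reported placebo mortality would go from 6/292 = 2.1% to 0/286 = 0%. The FAS may be smaller than the number randomized, but this hardly matters: with 280 per arm the p-values agree to within 0.0001.

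**Step 5. The safety table.** The treatment-emergent death window closes 30 days after the last dose. With dosing on Days 1 to 3, that is Day 3 + 30 = Day 33. Every death in a dosed participant by Day 28 would therefore be in the safety summary, while the same death could be missing from the efficacy table.

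**The case against.** Five points can be made for the plan.

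1. **The first condition has a proper use.** Death status is not defined as vital status at Day 28. A participant who withdraws alive on Day 10 could have a non-missing status and still be unknown at Day 28. This stands: the two-part structure does not show that the rule was aimed at deaths. It does not help with deaths, though, because the same words cover both groups.
2. **The primary analysis uses similar unqualified wording.** SAP 6.1.3 and Appendix 2 item 13 also begin with early discontinuation or missing status, and SAP 3.6.1 treats the primary rule as one for missing outcomes. That suggests a house shorthand for an outcome not observed, and it supports the benign reading of the intent. But 6.1.3 goes on to say how deaths are used, 6.1.4 adds a qualifier, and 6.2.1 does neither.
3. **The eCRF coding is unseen.** This stands. The missing exception is certain; the loss of deaths depends on how deaths were recorded.
4. **The sizes are hypothetical.** This stands. SAP 6.4 reports very few participants progressing to oxygen. That does not fix the number of deaths, but it gives no ground for presuming counts as high as 6 versus 0.
5. **The safety and efficacy tables may differ legitimately.** They use different windows and analysis sets, and the required listing of deaths would expose an omission. That makes an error detectable after the fact. It does not settle the derivation beforehand.

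**Conclusion.** The concern holds. As written, the rule in SAP 6.2.1 allows a recorded death before Day 28 to exclude the participant from the Day 28 mortality test, and no other section corrects this. The likely intent is a missing-outcome rule, and nothing in the documents shows that a death was actually dropped.

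The actual consequence depends on two things that the documents do not give: how deaths were coded on the Study Completion form, and how many occurred. On the assumed 292 per arm, the rule could reverse a significant result only with counts such as 6 versus 0 or 8 versus 1. With five or fewer deaths, all in one arm, it would falsify the reported counts and proportions but not the significance conclusion.

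The endpoint is exploratory, and deaths remain in the primary composite and in the safety summaries. This should be fixed, but it does not threaten the primary conclusion.

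**What to change.** Replace the exclusion sentence in SAP 6.2.1 with a rule to this effect: *Any participant with a recorded death by Day 28 is counted as a death, whatever the study completion status. Only participants with no recorded death and unknown vital status at Day 28, for example after withdrawing alive before Day 28, are excluded.* Because Protocol 6.5 allows the Day 28 visit a window of ± 5 days, add that a participant who completed that visit alive and has no recorded death counts as alive.

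The cost is one or two sentences and one derivation flag. If the SAP is already final, the clarification can be documented in the clinical study report, as SAP section 1 provides. A Kaplan-Meier estimate of Day 28 mortality, which would use the follow-up of those who withdrew alive, is optional.
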